6.2.6.3. Causality: Drug Relationship Assessment

The relationship of the event to the study drug should be determined by the investigator according to the following criteria:

- Definitely related: The event follows a reasonable temporal sequence from the time of drug administration that cannot be explained, follows a known or expected response pattern to the study drug, that is confirmed by improvement on stopping and reappearance of the event on repeated exposure and that could not be reasonably explained by other factors such as the patient's clinical condition, intercurrent illness, or concomitant drugs.
- Probably related: The event follows a reasonable temporal sequence from the time of drug administration, and/or follows a known response pattern to the study drug, and cannot be reasonably explained by other factors such as the patient's clinical condition, intercurrent illness, or concomitant drugs.
- Possibly related: The event follows a reasonable temporal sequence from the time of drug administration, and/or follows a known response pattern to the study drug, but could have been produced by other factors such as the patient's clinical condition, intercurrent illness, or concomitant drugs.
- Unlikely related: The event follows little or no temporal sequence from the time of drug administration that makes a causal relationship improbable and/or other factors such as the patient's clinical condition, intercurrent illness, or concomitant drugs is a more likely alternative.
- Not related: The event is most likely produced by other factors such as the patient's clinical condition, intercurrent illness, or concomitant drugs, and does not follow a known response pattern to the study drug, or the temporal relationship of the event to study drug administration makes a causal relationship unlikely.

6.2.6.4. Definition of Serious Adverse Events

A serious AE (SAE) is any AE that fulfills any of the following criteria, as per 21 CFR 312.32:

- Results in death;
- Is life-threatening;
- Requires in-patient hospitalization or prolongation of existing hospitalization;
- Results in persistent or significant disability or incapacity;
- Is a congenital anomaly or birth defect;
- Is medically significant or requires intervention to prevent one of the outcomes listed above.

Serious AEs will be captured from the time of consent through the end of the study.

6.2.6.5. Actions Taken

Actions taken may consist of:

- None
- Study drug discontinued
- Dose modified
- Required concomitant medication
- Required procedure
- Other

6.2.6.6. Outcome at the Time of Last Observation

The outcome at the time of last observation will be classified as:

- Recovered/resolved
- Recovered/resolved with sequelae
- Not recovered/not resolved
- Death
- Unknown

6.2.6.7. Adverse Event Recording and Reporting

Adverse events will be recorded throughout the study in the source documents and in the CRFs. The investigator will rate AEs for seriousness, intensity, causality, action taken, and outcome as described in the previous section.

Expedited reporting is required for serious unexpected adverse drug reactions. Fatal or life-threatening unexpected drug reactions must be reported by the Sponsor to regulatory agencies no more than 7 days after the Sponsor's first knowledge of the reaction; followed by as complete a report as possible within 8 additional days. Unexpected adverse drug reactions must be reported no later than 15 days after the Sponsor's first knowledge of the reaction. In order to comply with these requirements, the investigator or delegate must inform the Sponsor immediately upon occurrence of any SAE. The site will complete the SAE Report Form as thoroughly as possible and e-mail it to WCT within 24 hours of the investigators first knowledge of the event.

These SAE reports must contain the following information:

- A. Study name/number
- B. Study drug
- C. Investigator details (name, phone, fax, e-mail)
- D. Patient number
- E. Patient initials
- F. Patient demographics
- G. Clinical event

- 1) Description
 - 2) Date of onset
 - 3) Treatment (drug, dose, dosage form)
 - 4) Adverse event relationship to study drug
 - 5) Action taken regarding study drug in direct relationship to the AE
- H. If the AE was fatal or life-threatening
- I. Cause of death (whether or not the death was related to study drug)
- J. Autopsy findings (if available)

The Sponsor or its representative will be responsible for notification to regulatory agencies.

6.2.6.8. Adverse Event Follow-Up

All non-serious AEs that are not related or unlikely to be related to study treatment will be followed until the end of study participation. All SAEs or AEs that are considered as possibly, probably, or definitely related to treatment will be followed until resolution or stabilization.

6.2.6.9. Monitoring of AEs Potentially Related to Drug Metabolism

Cannabidiol inhibits drug metabolism mediated by a subset of CYP proteins (see [Section 1.1.2](#)). Thus, the Investigator and study center staff should monitor patients who are taking concomitant medications that are metabolized by CYP2C19, CYP2C9, CYP3A4, CYP1A2 or by P-glycoprotein with special care. Medication(s) that is/are strong inhibitor(s) or inducer(s) or sensitive substrates of CYP3A4 are exclusionary and prohibited (see [Sections 3.2.2](#) and [Section 4.7.2](#)). However, patients taking medications that are weak inhibitors or inducers of CYP3A4 should be monitored with special care.

6.2.6.10. Data Monitoring Committee

The Data Safety Monitoring Committee (DSMC) will consist of a least one physician with experience in treating IS subjects and at least one biostatistician. The DSMC ensures that the ethical principles are observed and monitors the safety of the subjects. To fulfil its responsibilities, the DSMC may have access to the clinical data. The DSMC may also meet on an ad hoc basis if needed. The DSMC will be informed to what extent the data and analyses provided to them have been quality controlled. Members of the DSMC will not be involved in other study-related tasks. The DSMC procedures are described in the Data Monitoring Committee Charter.

6.3. Pharmacokinetics Assessments

A blood sample for PK analysis of CBD and 7-OH-CBD will be obtained on Day 15 just prior to the second dose during the 24-hour video EEG. Whole blood will be obtained in a Vacutainer® tube containing K2-EDTA as a preservative.

7. STUDY PROCEDURES

The assessments and procedures that will be conducted during this study are summarized in [Table 1](#).

7.1. Screening Period (Visit 1)

Potential study patients will be examined before the start of the study to determine their eligibility for participation. Prior to performing any study related procedures or assessments, the Investigator will ensure that the patient's legal representative (parent[s]/caregiver[s]) provides written informed consent. Patients and their parent(s)/caregiver(s) will receive a copy of the ICF for review and must provide fully informed consent prior to study participation.

The following screening procedures and assessments are intended to be performed during Visit 1, but the patient may return to complete activities, which must be performed within 14 days of the start of the Initial Treatment Period for all patients.

- Obtain written informed consent.
- Review of inclusion and exclusion criteria (see [Sections 3.2.1](#) and [3.2.2](#)).
- Record demographic data.
- Record recent and concomitant medication and procedure history including vitamins, herbal preparations, blood products, and over-the-counter drugs. All medications taken ≤ 30 days of the Screening Visit must be documented in the concomitant medications section of the CRF.
- Record all prior and current anti-epileptic therapies (AETs, including drugs, ketogenic diet, vagal stimulators etc.)
- Record medical and surgical history.
- Record the types of seizures and the frequency of infantile spasms occurring ≤ 28 days of the Screening Visit based on parent/caregiver recollection.
- Record vital signs (seated or supine blood pressure [depending on patient age and ability], pulse rate, respiratory rate, and temperature measurements).
- Draw blood samples for hematology and chemistry.
 - o [Section 7.4](#) details the volume of samples to be drawn based on patient age.
- Perform a complete physical examination (see [Section 6.2.2](#)), including height, weight, and head circumference.
- Perform a complete neurological examination (see [Section 6.2.3](#)).
- Perform a minimum of 9-hr video-EEG that includes a full sleep-wake cycle.
- Completion of investigator CGI-S.
- Provide daily seizure diary to capture seizure activity (infantile spasms only) between visit 1 and visit 2, and train the caregiver to recognize and capture the infantile spasms.

7.2. Assessments and Procedures

7.2.1. Initial Treatment Period

7.2.1.1. Visit 2 (Day 1)

Once the patient has been approved for the study, they will return to the study clinic where the patient will be randomized to the appropriate treatment arm. Patients will receive the titration dose of vigabatrin (50 mg/kg/day divided twice daily [BID]), and either CBD 20 mg/kg/day plus matching CBD 20 mg/kg/day placebo or CBD 40 mg/kg/day placebo, each drug administered twice daily at 12-hour intervals for three days.

The following procedures and assessments will be performed during Visit 2:

- Review and record seizure diary.
- Record concomitant medications
- Record AEs.
- Perform a brief neurological examination predose (see [Section 6.2.3](#)).
- Administer the first titration dose of vigabatrin and the Investigational product and train caregiver(s) to measure, administer, and record doses.
- Vital signs will be taken after approximately 5 minutes seated or supine, depending on patient ability. Vital signs should be taken predose and at approximately 4 hours postdose.

7.2.1.2. Day 2 and Day 3

- The Investigator or designee will follow up by phone or E-mail for the first three days of the Initial Treatment Period, and record any AEs.
- Administer prescribed titration dose at approximately 12-hour intervals by the parent/caregiver.
- Parent/caregiver should also complete the seizure diary.

7.2.1.3. Visit 3 (Day 4)

Patients will receive 100 mg/kg/day divided twice daily of vigabatrin and (30 mg/kg/day CBD and CBD placebo 10 mg/kg/day or matching CBD 40 mg/kg/day placebo) divided twice daily for 3 days, according to the patient's assigned cohort. the following procedures and assessments will be performed on Day 4 for all patients prior to IP administration:

- Record concomitant medications
- Record vital signs (seated or supine blood pressure [depending on patient age and ability], pulse rate, respiratory rate, and temperature)
- Record height and weight.
- Perform a brief neurological examination predose (see [Section 6.2.3](#)).

- Draw blood samples for hematology and chemistry.
 - o [Section 7.4](#) details the volume of samples to be drawn based on patient age.
- Record AEs.
- Record and review daily seizure diary.
- Administer dose of vigabatrin and investigational product

The following activities will occur after administration of the morning dose of the investigational product:

- Perform an additional brief neurological examination approximately 2 hours postdose.
- Records AEs.

Patients will be released from the study center after assessments are complete.

7.2.1.4. Visit 4 (Day 7)

Patients will receive 150 mg/kg/day divided twice daily of vigabatrin and (40 mg/kg/day CBD day or matching CBD placebo) twice daily for 9 days, according to the patient's assigned cohort. The following procedures and assessments will be performed on Day 7 for all patients prior to IP administration:

- Record concomitant medications.
- Record vital signs (seated or supine blood pressure [depending on patient age and ability], pulse rate, respiratory rate, and temperature).
- Record height and weight.
- Perform a brief neurological examination predose (see [Section 6.2.3](#)).
- Draw blood samples for hematology and chemistry.
 - o [Section 7.4](#) details the volume of samples to be drawn based on patient age.
- Record AEs.
- Record and review daily seizure diary.
- Administer dose of vigabatrin and investigational product.

The following activities will occur after administration of the morning dose of the investigational product:

- Perform an additional brief neurological examination approximately 2 hours postdose.
- Records AEs.

7.2.1.5. Days 7-15

- Patients will receive 150 mg/kg/day divided twice daily of vigabatrin and (40 mg/kg/day CBD or matching CBD placebo) from Day 7 through Day 15. Doses will be administered at approximately 12-hour intervals by the parent/caregiver.
- Parent/caregiver should complete the seizure diary daily and note any adverse events. The investigator or designee will follow up by phone or e-mail on Days 9 to 11.

7.2.1.6. Visit 5 (Day 14)

On Day 14, patients will be admitted to the study center before the morning administration of vigabatrin and the investigational product and assessments. The following assessments will be completed PRIOR to administration of the morning dose of vigabatrin and the investigational product:

- Record concomitant medications.
- Record vital signs (seated or supine blood pressure [depending on patient age and ability], pulse rate, respiratory rate, and temperature measurements).
- Record height and weight.
- Perform a brief neurological examination (see [Section 6.2.3](#)).
- Record AEs.
- Record and review daily seizure diary.
- Start meal diary collection.

. The following assessments will be completed after administration of the morning doses of vigabatrin and the investigational product:

- Start the 24-hour video EEG assessment.

7.2.1.7. Visit 6 (Day 15, End of Study for the Initial Treatment Period)

The following activities will occur on Day 15, at approximately 24 hours post the Day 14 morning dose:

- Complete the 24-hour video EEG assessment.
- Record concomitant medications and AETs
- Record vital signs (seated or supine blood pressure [depending on patient age and ability], pulse rate, respiratory rate, and temperature measurements).
- Record height and weight and head circumference.
- Perform a complete neurological examination (see [Section 6.2.3](#)).
- Draw blood samples for hematology, chemistry and PK analysis. PK analysis will be obtained on Day 15 just prior to the second dose during the 24-hour video EEG.
 - o [Section 7.4](#) details the volume of samples to be drawn based on patient age.

- Record and review daily seizure diary.
- Record AEs.
- Completion of investigator CGI-I.
- Complete meal diary collection.
- Administer dose of vigabatrin and investigational product

Patients will be discharged from the study center after assessments are complete. Subjects will continue treatment until confirmation of treatment response after 24-hour video EEG and clinical laboratory results are received.

7.2.2. Taper Period

Following the completion of the Initial Treatment Period (Visit 6), partial responders who do not enroll in the open-label safety study and non-responders will have vigabatrin and CBD or CBD placebo tapered as follows:

- Vigabatrin taper: 150 mg/kg/day will be reduced to 100 mg/kg/day for 3 days, then 100 mg/kg/day will be reduced to 50 mg/kg/day for 3 days and then discontinued.
- CBD or CBD placebo taper: CBD: 40 mg/kg/day will be reduced to 30 mg/kg/day for 3 days, 30 mg/kg/day will be reduced to 20 mg/kg/day for 3 days, and then discontinued.

Complete Responders will be tapered off vigabatrin and CBD or CBD placebo at the completion of the Extended Treatment Period, and all patients will be tapered off at any Early Withdrawal Visits, using the same schedules as described above.

If the investigator decided to continue vigabatrin as a treatment for patients at the end of the study of at early withdrawal, tapering of vigabatrin will be left to the discretion of the PI.

CBD requires tapering off at the End of Study or at the Early Withdrawal visit. The following assessments will be performed during this period:

- Concomitant medications and AETs.
- Administer dose of vigabatrin and investigational product
- Record AEs.
- Record and review daily seizure diary.

7.2.3. Extended Treatment Period (Visit 7/Week 6, Visit 8/Week 10, and Visit 9/Week 13)

Following the Initial Treatment Period, Complete Responders will continue receiving their assigned treatments of vigabatrin plus either CBD 40 mg/kg/day or matching placebo for 75 days, until Week 13 (Day 90).

The following assessments and procedures will be completed at Visit 7 (Week 6), Visit 8 (Week 10), and Visit 9 (End of Study; Week 13):

- Record concomitant medications and AETs.

- Record vital signs (seated or supine blood pressure ([depending on patient age and ability]), pulse rate, respiratory rate, and temperature measurements).
- Record height, weight
- Head circumference (Visit 9, Week 13)
- Perform a brief neurological examination for Visits 7 and 8 and complete neurological exam for Visit 9 (EOS) (see [Section 6.2.3](#))
- Record AEs.
- Administer dose of vigabatrin and investigational product
- Draw blood samples for hematology and chemistry.
 - [Section 7.4](#) details the volume of samples to be drawn based on patient age.
- Record and review daily seizure diary.

In addition, a 9-hour video EEG will be performed to confirm parent/caregiver report of relapse. All patients will begin tapering off CBD and vigabatrin at the end of this period (Visit 9; see [Section 7.2.2](#)).

7.2.4. Partial Responders

Partial responders will be offered the opportunity to enroll in an open-label safety study that allows investigators to combine standard-of-care treatment with CBD or up to ..

7.2.5. Early Withdrawal Visit

Should a patient's participation be terminated prior to Day 14 or Day 90 for any reason (see [Section 3.3](#)), an Early Withdrawal Visit will be completed. The following procedures will be completed:

- Record concomitant medications and AETs.
- Record vital signs (seated or supine blood pressure ([depending on patient age and ability]), pulse rate, respiratory rate, and temperature measurements).
- Record height and weight and head circumference.
- Record and review daily seizure diary.
- Perform a complete neurological examination (see [Section 6.2.3](#)).
- Complete investigator CGI-I.
- Record AEs.
- Perform 9-hour video EEG, if possible only for patients that continued into the Extended Treatment Period.
- Draw blood samples for hematology and chemistry.
 - [Section 7.4](#) details the volume of samples to be drawn based on patient age.

All patients will begin tapering off investigational product and vigabatrin at this visit (see [Section 7.2.2](#)).

7.2.6. Follow-up Period

A follow-up phone call will occur for all subjects 30 days after discontinuation of the study drug to assess AEs, AETs, and record concomitant medications.

7.2.7. Follow-up of Adverse Events

Any AEs observed from the Screening Visit until the end of the study will be followed to resolution. Resolution means that the subject has returned to a baseline state of health or the Investigator does not expect any further improvement or worsening of the AE. All AEs that occur after the subject completed a clinical study should also be reported to the Sponsor within 30 days of the last dose of study drug.

7.3. Investigational Product PK Sample

A blood sample for PK analysis of CBD and 7-OH-CBD will be obtained while inpatient on Visit 6 (Day 15, EOS) just prior to the second dose during the 24-hour video EEG. A meal-diary will need to be completed on Visit 5 (Day 14) and Visit 6 (Day 15).

7.4. Sample Collection for Patients

The frequency for PK and safety laboratory samples has been adjusted to avoid excessive blood loss in a subset of patients. Multiple standards may be used to determine maximum acceptable blood loss in a clinical study. In this study, sample volumes will be adjusted for patients based on age to ensure that an excessive amount of blood is not removed. Two (2) metrics that are used to determine this volume are discussed below.

- As per the requirements of the Office for Human Research Protections, no more than 3 mL/kg per 8-week period should be removed.
- As per the National Institutes of Health, no more than 7 mL/kg per 6-week period should be removed.

Given the duration of this study, this effectively means that blood loss should not exceed approximately 3 mL/kg of body weight per patient for the entire study.

8. STATISTICS

The detailed descriptions of statistical analysis methods and data conventions will be in a separate document, the Statistical Analysis Plan (SAP). Any post-hoc analyses will be identified in the final clinical study report. This section presents general information about statistical considerations and concepts such as randomization, statistical power, and sample size. There will also be a brief discussion on analysis methodology, as well as some data conventions.

8.1. Study Endpoints

8.1.1. Primary Efficacy Endpoint

The primary efficacy endpoint in this study is:

- Percent of patients who are considered complete responders, defined as complete resolution of spasms and hypsarrhythmia, confirmed by 24-hour video EEG from Day 14 to Day 15, as determined by the Independent Central Reader.

8.1.2. Secondary Efficacy Endpoints

The secondary efficacy endpoints in the Initial Treatment Period of this study are:

- Percent of patients with resolution of infantile spasms as assessed by 24-hour video EEG from Day 14 to Day 15 (partial response).
- Percent of patients with resolution of hypsarrhythmia as assessed by 24-hour video EEG from Day 14 to Day 15 (partial response).
- Investigator impression of efficacy and tolerability of study drug (CGI-I) at Visit 6 (End of Study), or Early Withdrawal.
- Increase in the number of spasm-free days between Day 1 and Day 15 of the Initial Treatment Period, as determined by the seizure diary entries.
- For patients with a complete response during the Initial Treatment Period who continue: percent of patients who relapse during the Extended Treatment Period confirmed by video EEG following parent report of relapse, and time to relapse.

8.1.3. Safety Endpoints

The safety endpoints of this study are the incidence of treatment-emergent AEs (TEAEs), clinical laboratory assessments, vital signs (blood pressure, pulse rate, respiration rate, and temperature), physical and neurological examination assessments, medical history, and prior and concomitant medications, liver enzymes, and serum bilirubin.

8.2. Sample Size Determination

A total of 190 patients (130 and 60 patients in the two groups) will provide 80% power with a two-sided alpha of 0.05 to detect a difference in response rate, assuming the response with vigabatrin alone is 40% and the response with vigabatrin with Cannabidiol Oral Solution is 60%.

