If a patient discontinues the study prematurely, the investigator's impression of efficacy and tolerability of the study drug, as evaluated by CGI-I, will be assessed and recorded immediately before discontinuation. If possible, the parent/caregiver will be encouraged to have the patient have an Early Withdrawal video-EEG completed.

Number of patients planned:

Approximately 190 patients (130 patients in the active drug arm and 60 patients in the placebo arm).

Diagnosis and main criteria for inclusion:

Patients will be male and female patients between 1 and 24 months of age (inclusive), with a new clinical diagnosis of Infantile Spasms, confirmed by video-EEG analysis during the Screening Period, have adequate renal and hepatic function, and who meet all the inclusion and none of the exclusion criteria. Parent(s)/caregiver(s) must be able to understand and provide written consent.

Inclusion criteria

A patient will be eligible for study participation if the patient meets all of the following criteria:

1. Parent(s)/caregiver(s) fully comprehends and signs the informed consent form, understands all study procedures, and can communicate satisfactorily with the Investigator and study coordinator, in accordance with applicable laws, regulations, and local requirements.
2. Male or female between 1 month to 24 months of age (inclusive) at time of consent.
3. Clinical diagnosis of Infantile Spasms, confirmed by video-EEG (including at least one cluster of electroclinical spasms [≥ 3 in any 10-minute epoch] and hypsarrhythmia) obtained during the Screening Period and read by a central reader.
4. General good health (defined as the absence of any clinically relevant abnormalities as determined by the Investigator) based on physical and neurological examinations, medical history, and clinical laboratory values completed during the Screening Visit (Visit 1).
5. In the opinion of the investigator, the parent(s)/caregiver(s) is (are) willing and able to comply with the study procedures and visit schedules.

Exclusion criteria

A patient must not meet any of the following criteria:

1. Is considered by the investigator, for any reason (including, but not limited to, the risks described as precautions, warnings, and contraindications in the current version of the [Investigator's Brochure](#) for Cannabidiol Oral Solution) to be an unsuitable candidate to receive the study drug.
2. Known or suspected allergy to cannabidiol.

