- Investigator impression of efficacy and tolerability of study drug (CGI-I) at Visit 6 (End of Study) or Early Withdrawal.
- Increase in the number of spasm-free days between Day 1 and Day 15 of the Initial Treatment Period, as determined by the seizure diary entries.
- For patients with a complete response during the Initial Treatment Period who continue: percent of patients who relapse during the Extended Treatment Period confirmed by video EEG following parent report of relapse, and time to relapse.

Safety

The safety endpoints of the study are the incidence of treatment-emergent AEs (TEAEs), clinical laboratory assessments, vital signs (blood pressure, pulse rate, respiration rate, and temperature), physical and neurological examination assessments, prior and concomitant medications, liver enzymes and serum bilirubin.

Pharmacokinetics

Trough concentrations (C_{trough}) of cannabidiol (CBD) and 7-OH-CBD will be used to assess the exposure-response relationship. A meal diary will be used to record the type of meals consumed in relation to the PK blood draws.

Statistical methods:**Sample Size Calculation**

A total of 190 patients (130 and 60 patients in the two groups) will provide 80% power with a two-sided alpha of 0.05 to detect a difference in response rate, assuming the response with vigabatrin alone is 40% and the response with vigabatrin with Cannabidiol Oral Solution is 60%.

Analysis Populations

Statistical analyses will be conducted on the following populations:

- Safety Population: The Safety Population will include all patients who were treated with at least one dose of the study drug.
- Intent to Treat (ITT) Population: The ITT Population will include all patients who were randomized.
- PK Population: The PK Population will include all patients who were treated with at least one dose of the study drug and have at least one usable PK measurement.

Efficacy Analyses

The ITT Population will be used for all efficacy analyses in the Initial Treatment Period.

- For the primary endpoint, a 2-sided Type I error rate of 0.05 will be used.
- For the secondary efficacy endpoints, to maintain the trial-wise Type I error rate at 0.05, a fixed sequence multiple comparisons correction with fallback will be used. The assignment of alpha levels to hypotheses being tested will be specified in the Statistical Analysis Plan.

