8.4.3.1. Primary Efficacy Analysis

- Percent of patients with complete resolution of both infantile spasms and hypsarrhythmia at Day 15 (complete response) will be compared between vigabatrin plus placebo and vigabatrin plus CBD 40 mg/kg/day groups using a chi square test.

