### **3.3. Sample Size Calculation**

A total of 180 patients (120 patients in the 40 mg/kg/day arm and 60 patients in the placebo arm) will provide 80% power with a two-sided alpha of 0.05, assuming the response with vigabatrin alone is 40% and the response with vigabatrin with Cannabidiol Oral Solution is 62%.

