##### **10.6.1. Primary Efficacy Analysis**

The primary efficacy endpoint in this study is:

- Percent of patients who are considered complete responders, defined as complete resolution of spasms and hypsarrhythmia or a pattern of epileptic encephalopathy.

The percent of complete responders will be calculated for each treatment group and compared using Fisher's exact test.

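### The stated 80% power is not delivered: 130 vs 60 patients at 60% vs 40% give about 73% with the protocol's chi-square test and about 71% with the SAP's Fisher's exact test

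*Protocol*

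**What the plan says.** **Protocol.** Section 8.2 and the Synopsis (Sample Size Calculation) make the same claim: "A total of 190 patients (130 and 60 patients in the two groups) will provide 80% power with a two-sided alpha of 0.05". The alternative follows in the same sentence: "assuming the response with vigabatrin alone is 40% and the response with vigabatrin with Cannabidiol Oral Solution is 60" per cent. The Synopsis confirms the allocation as "130 patients in the active drug arm and 60 patients in the placebo arm". The primary comparison in Section 8.4.3.1 is between "vigabatrin plus placebo and vigabatrin plus CBD 40 mg/kg/day groups using a chi square test". Neither place mentions a continuity correction, a dropout allowance or a one-sided test.

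**SAP.** Section 3.3 and the Technical Summary Report size the trial differently: "A total of 180 patients (120 patients in the 40 mg/kg/day arm and 60 patients in the placebo arm) will provide 80% power", with 40% vs 62% as the assumed rates and a two-sided alpha of 0.05. For the primary test, Section 10.6.1 says: "The percent of complete responders will be calculated for each treatment group and compared using" Fisher's exact test.

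**The concern.** A design with 190 patients split 130/60 has less information than an equal split of the same total, and a 20-point difference around 50% usually needs close to 200 patients even when the arms are equal. An 80% claim at 13:6 allocation therefore looked too high.

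This sentence is the only justification the protocol gives for the size of a placebo-controlled Phase 3 trial in infants. A reader takes from it a 1-in-5 risk of missing the target effect. If the true risk is more than 1 in 4, the sponsor should accept that risk knowingly. In addition, the two documents attach the same 80% to different sample sizes, different effects and different tests, so it is unclear which power statement governs.

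**Working it through.** **Inputs** (all from Protocol 8.2, Synopsis and 8.4.3.1): n = 130 on CBD and 60 on placebo; rates 0.60 and 0.40; two-sided alpha 0.05 (z = 1.96); chi-square test.

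**Step 1. Try to reproduce the 80%.** Normal approximation with pooled variance under the null:

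- Pooled rate = (130 × 0.60 + 60 × 0.40) / 190 = 102 / 190 = 0.537
- se0 = √[0.537 × 0.463 × (1/130 + 1/60)] = 0.0778
- se1 = √[0.60 × 0.40/130 + 0.40 × 0.60/60] = 0.0765
- Power = Φ[(0.20 − 1.96 × 0.0778) / 0.0765] = Φ(0.62) = **73.3%**

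The 80% is not reproduced.

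**Step 2. Try other versions of the calculation**, same inputs. The exact figures sum the two binomial distributions over each test's rejection region.

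| Version, 130/60, 60% vs 40% | Power |
|---|---|
| Normal, pooled variance | 73.3% |
| Normal, unpooled variance | 74.4% |
| Arcsine | 73.2% |
| Normal, continuity-corrected | 67.8% |
| Exact, uncorrected chi-square | 73.0% |
| Exact, continuity-corrected chi-square | 68.6% |
| Exact, two-sided Fisher | 70.9% |
| One-sided alpha 0.05, pooled (not the plan) | 82.7% |
| Equal split 95/95, pooled (not the plan) | 79.2% |

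No two-sided version at the planned allocation reaches 75%. Only the equal split comes near 80%. The unequal allocation may therefore not have been carried into the calculation, but that is inference and the documents do not say so.

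**Step 3. What would give 80%?**

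- Same rates and about the same ratio, chi-square: 153 + 71 = 224 patients (80.2% by formula, 80.0% exact). Fisher needs more: 161 + 74 = 235 gives 80.7%.
- Same 130/60, 40% on placebo: the CBD rate must be about 61.7% with chi-square or about 62.3% with Fisher.

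**Step 4. The SAP's own case**, 120/60, 62% vs 40%:

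- Chi-square, pooled formula: 80.3%. This reproduces the SAP's 80%.
- Fisher, exact: 77.3%. This is the SAP's primary test.

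**Step 5. Missing EEGs (assumption).** Protocol 8.4.6 counts a patient without the Day 14-15 EEG as a non-responder, and no rate of missing EEGs is given. If the planning rates refer to patients with an EEG, and a share m is missing in each arm, both rates shrink by the factor (1 − m). Pooled chi-square power at 130/60 is then:

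| m | Rates | Power |
|---|---|---|
| 0 | 60% vs 40% | 73.3% |
| 5% | 57% vs 38% | 68.7% |
| 10% | 54% vs 36% | 64.0% |
| 15% | 51% vs 34% | 59.3% |

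If the 60% and 40% already allow for missing EEGs, the first row applies.

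**The case against.** The arithmetic is not in dispute, but several points can be made about its reach.

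- *The 71% mixes documents.* It applies the SAP's test to the protocol's numbers, a combination neither document plans. This is fair as a matter of labelling: the protocol's own error is 73% against 80%, and 71% applies only if Fisher's test is used on the current design. It stays relevant because the SAP names that test for the primary analysis.
- *The mismatch is version lag.* SAP Section 1 ties the SAP to protocol V2.0 of 30 October 2017 and expects updates for amendments. The SAP also differs from the current protocol on age range, EEG days and other design features. That plausibly explains the different sample size, rate and test. It does not correct Section 8.2, which fails on its own inputs.
- *The SAP is only slightly off.* Its 80% holds for chi-square, and it does not say which test the power refers to. The shortfall under Fisher is about 3 points.
- *The missing-EEG loss is assumed.* This is true, and the conclusion does not depend on it.
- *Trial validity is untouched.* The type I error and the analysis are unaffected. What is wrong is the stated basis for the sample size, and that is still a factual error in the protocol.
- *Restating the alternative as 62% fits the assumption to the sample size.* This stands as a caution. The documents give no reason to prefer 62% over 60%, so a sponsor taking that route should supply one.

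**Conclusion.** The concern holds. On the protocol's own inputs, power is about 73% with the uncorrected chi-square test, a shortfall of about 7 points. With the SAP's Fisher test on the same design it is about 71%, a shortfall of about 9 points. The type II error is 27% to 29% instead of 20%. The result rests only on figures stated in the protocol, namely the arm sizes, the two rates and two-sided alpha 0.05, and on complete outcome classification of all randomized patients. Losses from missing EEGs, if not already in the planning rates, would lower it further. The SAP's 80% does not rescue the claim, because it belongs to a different sample size and effect and falls to 77.3% under the SAP's own primary test.

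**What to change.** In Protocol Section 8.2 and the Synopsis, make one of two changes:

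1. Keep 130/60 and 60% vs 40%, and state the power as about 73% (two-sided alpha 0.05, uncorrected chi-square).
2. Keep 130/60 and 80% power, state the detectable response as about 62% vs 40% (61.7% with chi-square, 62.3% with Fisher), and give a reason for that rate.

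If the sponsor instead wants 80% power for 60% vs 40%, the total becomes 224 with chi-square. That is a design decision and is not needed to correct the statement.

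Put the same sample size, rates and test in the SAP's Technical Summary Report and Section 3.3. Name one primary test, including whether a continuity correction is used, in the Synopsis, Protocol 8.4.3.1, the Technical Summary Report and SAP 10.6.1. The power statement should name that test and say whether the planning rates already count missing EEGs as non-response.

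The cost is wording in two protocol places and two SAP places for the power statement, plus agreement on the test. With either change, no extra patients are needed. The sponsor has to show a less favourable power or a larger detectable effect.
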